14.3 Tertiary Endpoint

14.3.1 Real-world treatment patterns

Tertiary endpoints collected retrospectively or at Study Visit 1 will be analyzed descriptively as defined in Section 8. Time, type, and reason for first sequential treatment after first course of IMP, type of second sequential treatment, as well as the frequency of routine clinical monitoring and disease activity status. The “physician sequential treatment decision questions” eCRF page will be used to analyze first and second sequential treatment (by DMD type only). The “frequency stable patient monitoring questions” eCRF page will be used for the frequency of routine clinical monitoring.

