Time-to-event data will be calculated from first dose of IMP in the parent study and will be presented using Kaplan-Meier estimates or cumulative incidence curves as appropriate. The analytical approach will be further detailed in the SAP.

Genetic variations will be analyzed descriptively. In addition, association of genetic variations with patients experiencing long-term response will be analyzed.

Adverse events will be summarized by number and frequency of patients with events.

Endpoint	Statistical Analysis Methods
Primary	Percentage and 95% CI
Secondary	Percentage and 95% CI
Tertiary/Exploratory	Descriptive statistics and time-to-event analyses as described above

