9.5 Handling of missing data/ Presentation of continuous and qualitative variables

It is anticipated that missing/not reported data will feature many of the endpoints, especially BVMT-R and SDMT (see section 14.3.3). No imputation will be done for these assessments.

In general, missing or partial dates will be imputed as follows:

- If year and month available but day is missing, impute day to 15
- If only year available, impute day and month to 15JUN
- If date is completely missing, then no imputation will be done, except for Concomitant Medication end dates: if end date is completely missing (day, month and year) and partial or complete start date then end date will be imputed to be the last study assessment date.

In addition, for concomitant medication dates:

- If imputed start date is after end date, then the start date will be set equal to end date.
- If imputed end date is before start date, then the end date will be set equal to start date.

For time to event analyses, if partial date does not determine whether event occurred before or after start date, then analysis date will be set equal to start date, subject will be censored and time to censoring = 1/365.25.

Continuous variables:

Continuous variables will be summarized using descriptive statistics, i.e.

- number of subjects (N),
- number of subjects with non-missing values,
- number of subjects with missing values
- mean and standard deviation,

- median, 25th Percentile - 75th Percentile (Q1-Q3),
- minimum, and maximum.

Qualitative variables:

Qualitative variables will be summarized by counts and percentages.

There are no plans for any formal statistical inference. This study will adhere to the Guidelines for Good Pharmacoepidemiology Practices (GPP). Data evaluation and interpretation will be based on point estimates and 95% corresponding confidence intervals (CI). Due to the exploratory nature of the study, an adjustment for multiple comparisons is not required.

Analyses will be performed using SAS® Software version 9.4 or higher.

10 Study Participants

The subsections in this section describe the specifications for reporting participant disposition and study discontinuations.

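### Time to first subsequent DMD has no time-to-event analysis in SAP 14.3.1; the natural default summary would cover only patients who started a DMD and would be too short

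*SAP*

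**What the plan says.** SAP 14.3.1 covers "Time, type, and reason for first sequential treatment after first course of IMP, type of second sequential treatment", together with monitoring frequency and disease activity status. The method is one sentence: "Tertiary endpoints collected retrospectively or at Study Visit 1 will be analyzed descriptively as defined in Section 8". SAP Section 8 defines populations and subgroups and holds no summary rule. The SAP's general rule is in 9.5: "Continuous variables will be summarized using descriptive statistics". It lists N, non-missing and missing counts, mean and SD, median and quartiles, minimum and maximum.

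Protocol 9.4 says two things. It states that tertiary endpoints gathered from charts or at Study Visit 1 are analysed descriptively. It then says that time-to-event data, measured from first dose of IMP, "will be presented using Kaplan-Meier estimates or cumulative incidence curves as appropriate", and leaves further detail to the SAP. Its closing method table gives tertiary endpoints "Descriptive statistics and time-to-event analyses as described above".

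The SAP specifies Kaplan-Meier once, in 14.3.2, for first use of an ambulatory device or wheelchair (Table 15.2.6.2, Figures 15.2.6.1 and 15.2.6.2). The treatment-pattern objective has one efficacy output, Table 15.2.5.1. SAP 7 records no change from the protocol's analyses.

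**The concern.** A patient who has not started a DMD by Study Visit 1 has no start date. In a time-to-event analysis that patient is censored and stays in the risk set until then. In a 9.5 summary the only visible place for the patient is "number of subjects with missing values". The time summary is then conditional on having started, so it is shorter than the time for all patients. It also reacts weakly to the number who never needed another drug.

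Protocol 2.3 puts treatment sequencing in the study's primary aim, and Protocol 4.2 calls it a data gap. A published starters-only median could easily be read as how long patients go before needing another therapy.

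**Working it through.** **Is there a figure to reproduce?** No. Neither document states an expected time to first DMD or an expected DMD-free share.

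**Is there a censoring rule elsewhere in the SAP?** The time-to-event sentence in 9.5 covers only a partial event date that cannot be placed before or after the start date. It gives no censoring date for a DMD-free patient and no rule for death before a DMD. Sections 8.2.2, 12 and 14.3.1 give none either.

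**Direction.** Let F(t) be the probability of starting a DMD by time t, and let follow-up be C years. Among starters, the probability of having started by t is F(t)/F(C). For t < C this exceeds F(t) whenever F(t) > 0 and F(C) < 1. With a common follow-up time, starters' times are therefore shorter for any distribution.

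**Size, illustrative.** Inputs:
- C = 10 years. Protocol 9 puts the visits around 10 years after initial treatment.
- DMD-free share at year 10, S = 30%, 50% or 70%. This is an assumption.
- Constant hazard h = -ln(S)/10. This is an assumption.

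All-patient median = ln 2 / h. Starters' median = -ln(1 - (1 - S)/2) / h.

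| S | h per year | All-patient median | Starters' median |
|---|---|---|---|
| 30% | 0.1204 | 0.6931/0.1204 = 5.8 y | -ln(0.65)/0.1204 = 3.6 y |
| 50% | 0.0693 | 0.6931/0.0693 = 10.0 y | -ln(0.75)/0.0693 = 4.2 y |
| 70% | 0.0357 | not reached by year 10 | -ln(0.85)/0.0357 = 4.6 y |

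Means behave the same way. At 30%, 50% and 70% DMD-free, the starters' mean is 4.0, 4.4 and 4.7 y. The mean restricted to 10 years, over all patients, is 5.8, 7.2 and 8.4 y. From 30% to 70% DMD-free the restricted mean rises by a factor of 8.41/5.81 = 1.45, and the starters' mean by only 4.70/4.02 = 1.17.

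**Range.**
- Weibull shape 0.7 to 1.5 instead of constant hazard, still at 10 years: the starters' median is 2.3 to 5.0 y against 4.5 to 6.9 y at 30% DMD-free, 2.9 to 5.6 y against 10.0 y at 50%, and 3.3 to 5.9 y against not reached at 70%.
- Both medians scale with follow-up. At 15 years with constant hazard and 30% DMD-free they are 5.4 and 8.6 y.
- Simulation with 587 patients (the 30% recruitment row of Protocol 9.2), constant hazard and follow-up spread evenly over 8 to 13 years: the starters' median is about 3.7, 4.0, 4.3 and 4.5 y at 30%, 40%, 50% and 60% free at year 10. Kaplan-Meier recovers 5.8, 7.6 and 10.0 y for the first three. At 60% its median is reached in only 28% of runs.

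**Time origin.** The SAP and protocol do not agree on where the clock starts:
- SAP 14.3.1: after the first course.
- Protocol 9.4: first dose, for time-to-event data in general.
- SAP 12: DMDs after first and after last cladribine dose, ordered by date from first dose of IMP.
- SAP 8.2.2, DMD-type subset: after last dose of IMP.

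The choice matters. For a CLARITY-EXT patient, 96 weeks of CLARITY plus the median 41-week gap is 137 weeks, about 2.6 years (137 × 7 / 365.25), before extension dosing begins.

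**The case against.** The strongest reply is that nothing wrong has actually been chosen. The SAP sentence closely follows Protocol 9.4, which also says descriptively. In SAP 14.3.2 the same word introduces a list of endpoints, some of which then receive Kaplan-Meier. The SAP says it is based on protocol section 9 and declares no changes, so Kaplan-Meier could be taken as inherited. Protocol 9.4 starts its clock at first dose, which fits the mobility endpoints better than an endpoint defined after the first course.

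Much of the durability information also appears elsewhere. DMD-free patients have their own category in the DMD-type subset. Responder definition B gives a 4-year landmark from last dose, and SAP 11.1 tabulates it by exposure group for each cohort. Tables 15.1.7.2 to 15.1.7.15 report subsequent DMDs and switching patterns.

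Part of this stands. A reader might infer that the SAP contradicts the protocol outright, or that it states a starters-only summary. The documents support neither: the protocol's text points both ways, and the SAP is silent on DMD-free patients. Nor is the DMD-free information lost altogether.

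What remains is that 14.3.2 goes on to spell out Kaplan-Meier, whereas 14.3.1 adds no such step and the output list contains no such table or figure. A count without a time axis and a single landmark from a different origin do not give the time distribution that the endpoint names.

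**Conclusion.** The point holds as a gap in method and output for one component of a tertiary, exploratory endpoint. Followed as written, with the 9.5 summaries, SAP 14.3.1 gives a time to first DMD that is biased short. The direction follows from conditioning on having started. That DMD-free patients would be counted as missing is an inference from the text, though the most natural one.

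The size rests on an assumed DMD-free share of 30% to 70%, and the central figures also on a constant hazard and 10 years of follow-up. On that basis the starters' median is 3.6 to 4.6 y, against 5.8 y to not reached. A reader might go further and say the true median more than triples over that range. That would need a median of ln 2 / 0.0357 = 19.4 y at 70% DMD-free, well beyond the follow-up, which the study could not report. Not reached is the supportable statement.

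The SAP should be amended. The point does not touch the primary or secondary endpoints.

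**What to change.** In SAP 14.3.1:
- Define the start of the first subsequent DMD as the event, and reconcile the time origin across SAP 14.3.1, SAP 12, SAP 8.2.2 and Protocol 9.4.
- Censor DMD-free patients at Study Visit 1 or last chart contact, and treat death before a DMD as a competing event. Deceased patients enter only by proxy consent or waiver, so such deaths may be few, but a rule is still needed.
- Report cumulative incidence with 95% CI at 2-year steps in all FAS patients, by exposure group and parent study.
- Add one table and one figure under 15.2.5 in Appendix 17.1.
- Correct the reference from Section 8 to 9.5 for the remaining descriptive items.
- Label any starters-only time summary as conditional on having started.

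The cost is SAP wording and a little programming. The DMD dates are already needed for the responder definitions, and the 14.3.2 code already assumes a time-to-event dataset. No new data collection is needed.

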14.3.2 Durability of clinical outcomes

Durability of clinical outcomes will be summarized descriptively and evaluated via retrospective data collection from medical records or at Study Visit 1:

- Proportion of study participants being bedridden
- Time from first dose of IMP to first use of an ambulatory device
- Time from last dose of IMP to first use of an ambulatory device
- Time from first dose of IMP to first use of a wheelchair
- Time from last dose of IMP to first use of a wheelchair
- Number of MS relapses between the end of parent study to Study Visit 1
- ARR from time of first dose of IMP to SV1, and by 2-year intervals
- ARR from time of last dose of IMP to SV1, and by 2-year intervals
- % and Time to conversion to CDMS (For Cohort D participants only)
- Proportion of study participants diagnosed as Secondary Progressive MS (SPMS) without relapses in the 3 months prior to SPMS diagnosis
- Proportion of study participants diagnosed as SPMS with relapses in the 3 months prior to SPMS diagnosis
- Proportion of study participants diagnosed as Primary Progressive MS (PPMS) (For Cohort D participants only)

Computational rule:

Participants being bedridden, first use of an ambulatory device and first use of a wheelchair are collected on “ambulatory - bedridden status and first use of wheelchair” eCRF page.

Participants diagnosed as SPMS with and without relapses in the 3 months prior to SPMS diagnosis are collected on “History of MS onset” eCRF page and Participants diagnosed as PPMS are collected on “conversion to CDMS” eCRF page.

Time to first ambulatory device/wheelchair

Kaplan Meier curve and estimates including number of subjects at risk, number of subjects with an event and subject censored will be presented for time to first ambulatory and wheelchair from first and last dose of IMP administered, by treatment group (exposed vs never exposed) and overall

Computation rule:

Whichever come first will be considered as an event:

- 1) CRF Ambulatory device page, wheelchair use date
- 2) CRF Ambulatory device page, ambulatory device use date
- 3) EDSS score ≥ 6
- 4) Death due to MS

Kaplan Meier SAS code:

AVAL = time-to-event response variable

CENSOR = censoring variable (0 = event, 1 = no event)

TRT= Trt group (“Exposed to Clad” “Never exposed to Clad”)

Code:

```
PROC LIFETEST DATA=ADTTE OUTSURV=RESULTS ALPHA=0.05 METHOD= KM Conftype =  
Loglog;  
TIME AVAL*CENSOR(1);  
STRATA TRT;  
RUN;
```

Annualized Relapse Rate:

ARR from time of FDIMP to Study Visit 1 is calculated for each treatment group:

$$\text{ARR} = [(\text{sum of relapses} * 365.25) / (\text{sum of time on study in days until SV1})]$$

ARR from time of FDIMP to Study Visit 1 and by 2-year intervals is calculated for each treatment group:

$ARR = [(sum\ of\ relapses\ *365.25) / (sum\ of\ time\ on\ main\ study\ by\ 2\text{-}year\ intervals\ in\ days\ until\ SV1)]$

Time on study = Study Visit 1 – first dose of IMP +1

ARR from time of last dose of IMP to Study Visit 1 will be calculated similarly.

Table 5: Time window for ARR by 2-year intervals

Cumulative intervals	Time intervals
Less than 2 years	1 to 730 days
2 nd years to 4 th years	731 to 1461 days
4 th years to 6 th years	1462 to 2191 days
6 th years to 8 th years	2192 to 2922 days
X th years to Y th years...	Truncate (X*365.25 +1) to truncate (Y*365.25) days

Time to CDMS (Cohort D only)

Number of participants who converted to CDMS since first and last dose administered will be summarized descriptively.

Both information collected in “Conversion to CDMS” eCRF page and ORACLE MS parent study dataset will be used to identify participants who converted to CDMS after first/last dose of IMP.

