6.1 Summary of CLASSIC MS

This Phase IV, low-interventional, multicenter, ambispective study will involve the evaluation of medical records of study participants treated with Cladribine Tablets or placebo (IMP) in the previously conducted parent studies. Long-term retrospective data will be collected through evaluation of medical charts/records, and additional prospective data will be collected. No IMP will be administered as part of this study. A total of 1943 patients has been enrolled in the parent studies, 1326 from CLARITY (including 867 enrolled in CLARITY-EXT) and 617 from ORACLE MS. This study will collect data from study participants with MS who participated in the CLARITY/CLARITY-EXT clinical trial(s) and who received ≥ 1 course of IMP, or study participants with their First Clinical Demyelinating Event (FCDE) who were randomized in the ORACLE MS study and received ≥ 1 course of IMP.

Participants are invited to up to 3 clinic visits for this study. The first visit is the Screening Visit.

The following screening activities may be administered by telephone if the patient is unable and/or not willing to attend clinic for the visit, depending on approval by Ethics Committees (ECs), Institutional Review Boards (IRBs), and/or local regulations: Informed consent (for patients participating in retrospective data collection only, local requirements for patient consent will be observed, which may include informed consent form [ICF] waiver), sociodemographic and clinical characteristics, medical and disease history, and study inclusion/exclusion determination.

Figure 1: CLASSIC study Overview Diagram

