6.2 Summary of Parent Studies

CLARITY (25643): The CLARITY (CLAdRibine Tablets treating MS orally) study was a multicenter, randomized, double-blind, three treatment group study of 96 weeks duration. Depending on their body weight, subjects took 1 or 2 cladribine 10 mg tablets (or matching placebo) per day over 4 to 5 days in either (a) Week 1 and Week 5 of Years 1 and 2, or (b) in Weeks 1, 5, 9, and 13 of Year 1, followed by Weeks 1 and 5 of Year 2, for a cumulative dose of 3.5 and 5.25 mg/kg, respectively. The primary objective of the trial was to evaluate the efficacy of cladribine versus placebo in the reduction of qualifying relapse rate during 96 weeks of treatment in subjects with RRMS. The secondary objectives were to assess the effect of cladribine on progression of disability (EDSS) and lesion activity as measured by MRI.

CLARITY EXT (27820): The CLARITY EXT (CLAdRibine Tablets treating MS orally EXTension) study was a randomized, double-blind, 96-week Extension study to evaluate the long-term safety and efficacy of oral cladribine in subjects with RRMS who had completed the CLARITY study. In the CLARITY EXT study, only the lower dose of cladribine was administered (subjects took 1 or 2 cladribine 10 mg tablets (or matching placebo) per day over 4 to 5 days in Week 1 and Week 5 of Years 1 and 2, for a cumulative dose of 3.5 mg/kg). Subjects who were assigned to the placebo arm in CLARITY were assigned to cladribine treatment. Subjects who received cladribine in CLARITY were randomized to either placebo or cladribine 3.5 mg/kg treatment groups in a 1:2 ratio, creating 5 arms:

Cladribine high/low dose (HLLL): Subjects who were randomized to cladribine high dose with 1 or 2 cladribine 10 mg tablets per day over 4 to 5 days in Weeks 1, 5, 9, and 13 of Year 1, followed by Weeks 1 and 5 of Year 2 of the CLARITY study (25643) (total dose 5.25 mg/kg), and to cladribine low dose with 1 or 2 cladribine 10 mg tablets per day over 4 to 5 days in Week 1 and Week 5 of Years 1 and 2 of the CLARITY extension study (total dose 3.5 mg/kg).

Cladribine low/low dose (LLLL): Subjects who were randomized to cladribine low dose with 1 or 2 cladribine 10 mg tablets per day over 4 to 5 days in Week 1 and Week 5 of Years 1 and 2 of the CLARITY study (25643) (total dose 3.5 mg/kg), then to cladribine low dose with 1 or 2 cladribine 10 mg tablets per day over 4 to 5 days in Week 1 and Week 5 of Years 1 and 2 of the CLARITY extension study (total dose 3.5 mg/kg).

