INTERFERON BETA-1B Betaferon, Extavia???	L03AB, Interferons	Interferons
MITOXANTRONE HYDROCHLORIDE	L01DB, Anthracyclines and related substances	Antineoplastic anthracyclines and related substances BCRP inhibitors BCRP substrates
PEGINTERFERON BETA-1A	L03AB, Interferons	Interferons

13 Study Treatment: Compliance and Exposure

Not Applicable.

14 Efficacy Analyses

No formal statistical hypothesis will be tested, as the study is designed to be exploratory. All analyses will be performed by parent study treatment group and for cohort A except when otherwise specified. In case of low number of participants within a subgroup category as described in section 8.2.2, the subgroup analysis will not be performed for the corresponding efficacy analysis.

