Table 15.2.4.4.1	MRI characteristics at Study Visit 2 of long-term responders vs non-responders – Cohort D- MRISS analysis set		
Table 15.2.4.4.2	MRI characteristics at Study Visit 2 of long-term responders vs non-responders – Cohort D – MRISS analysis set (Sensitivity Def B)		
Table 15.2.4.4.3	MRI characteristics at Study Visit 2 of long-term responders vs non-responders – Cohort D – MRISS analysis set (Sensitivity Def C)		

15.2.5: Tertiary Endpoint 1			
Table 15.2.5.1	Real-world treatment patterns in study participants – Cohort A- FAS analysis set		U
15.2.6: Tertiary Endpoint 2			
Table 15.2.6.1	Durability of clinical outcome– Cohort A – FAS analysis set		U
Table 15.2.6.2	Kaplan Meier- Time to first ambulatory device/wheelchair - Cohort A -FAS analysis set	Y	U
Figure 15.2.6.1	Kaplan Meier- Time to first ambulatory device/wheelchair by Exposed/Never Exposed Group - Cohort A -FAS analysis set	Y	U
Figure 15.2.6.2	Kaplan Meier - Time to First Ambulatory Device/Wheelchair - Cohort A - FAS Analysis Set	Y	
15.2.7: Tertiary Endpoint 3			
Table 15.2.7.1	Change in Quality of life outcomes – Cohort A- FAS analysis set	Y	U
Table 15.2.7.2	Change in Cognition outcomes (BVMT-R score)– Cohort D- FAS analysis set		U
Table 15.2.7.3	Change in Cognition outcomes (SDMT score) – Cohort D- FAS analysis set		U
15.2.8: Tertiary Endpoint 4			
Table 15.2.8.1	Change in MRI assessment from Baseline to Study Visit 2– Cohort A -MIRISS analysis set		U
15.2.9: Tertiary Endpoint 5			
Table 15.2.9.1	Responder rate by HDA/Non-HDA patients – Cohort B-FAS analysis set		U
15.2.10: Additional analysis			
Table 15.2.10.1	Additional analysis: Comparison between baseline characteristics from Non-CLASSIC/CLASSIC patients- WPS analysis set		U
15.2.11: PGX Analysis (tables will be repeated for each SNP or combination of SNPs.)			
Table 15.2.11.1.1	Proportion of patients using a wheelchair (EDSS>=7) the majority of the time in the 3 months prior to Study Visit 1 or bedridden – Cohort A – Subgroup with Presence of SNP1 gene - PGX Population		
Table 15.2.11.2.1	Proportion of patients with EDSS of 6.0 or higher since last dose of IMP – Cohort A – Subgroup with Presence of SNP1 gene - PGX Population		

Table 15.2.11.3.1	Clinical characteristics at Study Visit 1 of long-term responders vs Non-Responders – Cohort A– Subgroup with Presence of SNP1 gene - PGX Population		

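### The exposed versus never-exposed Kaplan-Meier, relapse-rate, bedridden and SPMS outputs are planned only for pooled Cohort A, with no allowance for parent trial, so the contrast can be confounded by trial mix

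*SAP*

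**What the plan says.** SAP 14 sets the default: "All analyses will be performed by parent study treatment group and for cohort A except when otherwise specified". SAP 14.3.2 then gives the Kaplan-Meier analysis "by treatment group (exposed vs never exposed) and overall", and its code stratifies on the treatment variable alone. For relapses, "ARR from time of FDIMP to Study Visit 1 is calculated for each treatment group", as total relapses over total time.

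The output list in SAP Appendix 17.1 follows this. Table 15.2.6.1 is titled "Durability of clinical outcome– Cohort A – FAS analysis set". Figure 15.2.6.1 is titled "Kaplan Meier- Time to first ambulatory device/wheelchair by Exposed/Never Exposed Group - Cohort A -FAS analysis set". Table 15.2.6.2 and Figure 15.2.6.2 are also for Cohort A. No Cohort B, C or D version of these outputs is listed.

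Other endpoints are treated differently:
- The primary endpoint's Cohort A logistic model includes parent study (SAP 14.1), and the endpoint is tabulated for Cohorts A, B, C and D.
- The EDSS 6.0 or higher endpoint is also tabulated for Cohorts A to D.
- CDMS conversion and PPMS diagnosis are restricted to Cohort D, so they are not pooled.

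Protocol 9.3 allows selected tertiary analyses to be repeated by Cohorts B, C and D to check consistency across trials. The SAP does not take this up for the outputs discussed here.

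**The concern.** CLARITY enrolled established relapsing-remitting MS; ORACLE MS enrolled patients after a first demyelinating event. Their long-term disability and relapse risks are likely to differ. If the exposed and never-exposed groups draw on the two trials in different proportions, a pooled curve or ARR can show a gap between groups even when cladribine has no effect.

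The parent designs make different proportions likely. On CLARITY-EXT, SAP 6.2 states: "Subjects who were assigned to the placebo arm in CLARITY were assigned to cladribine treatment". SAP 8.2.1 counts anyone with at least one cladribine dose as exposed, so CLARITY's contribution to the never-exposed group is essentially its placebo patients who did not enter the extension. An ORACLE MS placebo patient leaves that group only by receiving open-label cladribine.

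Interpretation is what is at stake. Table 15.2.6.2 and both figures are flagged for the interim analysis, whose results SAP 6.4 says have been disseminated. The SAP's caution against reading a treatment effect (SAP 8.2.2) names the treatment-course and subsequent-DMD subgroups, not the exposed versus never-exposed split.

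**Working it through.** **Inputs from the documents.** SAP 6.1: "A total of 1943 patients has been enrolled in the parent studies, 1326 from CLARITY (including 867 enrolled in CLARITY-EXT) and 617 from ORACLE MS". Check: 1326 + 617 = 1943. CLARITY-EXT entry: 867/1326 = 65.4%.

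**Assumptions.** The documents give no exposure-by-trial counts and no trial-specific risks, so I assume:
- equal 1:1:1 allocation in both trials;
- CLARITY-EXT entry e in the placebo arm equal to the overall 65.4%, with all those entrants treated with cladribine;
- a share x of ORACLE MS placebo patients given open-label cladribine, taken as 0-50%;
- the same recruitment fraction into CLASSIC-MS from each trial and exposure group.

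**Trial mix.**
- CLARITY never exposed = (1326/3)(1 − e) = (1326 − 867)/3 = 153; exposed = 1326 − 153 = 1173.
- ORACLE MS never exposed = (617/3)(1 − x): 206 at x = 0 and 103 at x = 50%; exposed = 411 and 514.
- ORACLE MS share of never exposed: 206/(206 + 153) = 57.3% at x = 0; 103/(103 + 153) = 40.2% at x = 50%.
- ORACLE MS share of exposed: 411/(411 + 1173) = 26.0%; 514/(514 + 1173) = 30.5%.

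**Spurious contrast with no drug effect.** If f is a group's ORACLE MS share, its pooled risk = f × (ORACLE MS risk) + (1 − f) × (CLARITY risk). The ratio is exposed over never exposed.

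| Uptake x | ORACLE MS share, never / exposed | Risks 10% CLARITY, 2% ORACLE MS: never / exposed (ratio) | Risks 15%, 5%: never / exposed (ratio) |
|---|---|---|---|
| 0% | 57.3% / 26.0% | 5.4% / 7.9% (1.46) | 9.3% / 12.4% (1.34) |
| 25% | 50.2% / 28.3% | 6.0% / 7.7% (1.29) | 10.0% / 12.2% (1.22) |
| 50% | 40.2% / 30.5% | 6.8% / 7.6% (1.11) | 11.0% / 12.0% (1.09) |
| 65.4% | 31.8% / 31.8% | 7.5% / 7.5% (1.00) | 11.8% / 11.8% (1.00) |
| 80% | 21.2% / 32.9% | 8.3% / 7.4% (0.89) | 12.9% / 11.7% (0.91) |

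Over x = 0-50%, the 10%/2% case gives a gap of 2.5 down to 0.8 percentage points. The Kaplan-Meier event is broader than the primary endpoint, because it includes any ambulatory device and EDSS of 6 or more, so higher risks are possible. Doubling 15%/5% to 30%/10% leaves the ratios unchanged and gives gaps of 6.3 down to 1.9 points.

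**Where the conclusion turns.** The mixes are equal when x = e, because both groups then hold ORACLE MS at 617/1943 = 31.8%. Above that, the direction reverses. ORACLE MS is a majority of the never-exposed only if (617/3)(1 − x) > 153, that is x < 25.6%.

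**Sensitivity to extension entry.** At e = 50% the shares are 48.2% versus 27.1% (x = 0) and equal at x = 50%. At e = 80% they are 69.9% versus 24.9% (x = 0) and 53.8% versus 29.4% (x = 50%).

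**The case against.** The other side has several fair points.

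- **Overlapping trial-specific outputs.** EDSS 6.0 or higher, which is one of the Kaplan-Meier event triggers, and the wheelchair/bedridden composite already have Cohort A to D tables. SAP 10.1 gives exposure-group numbers by cohort, so readers can see the mix. This stands. What lacks a trial-specific version is timing, ARR, SPMS and stand-alone bedridden status. Seeing the mix in a disposition table does not correct a pooled curve.
- **Weight.** These are descriptive tertiary outputs in an exploratory study with no hypothesis test and no planned hazard ratio. Protocol 9 says population differences will be considered when drawing inferences. This limits the point to interpretability; error control is not affected.
- **Precision.** At 30% recruitment the never-exposed group would be about 77-108 patients (0.3 × 256 to 0.3 × 359). With the 10%/2% risks, the Wald 95% half-width for its risk is then about 5.6 to 4.3 points, wider than the 0.8 to 2.5-point artefact. This also stands for that scenario, although larger risk differences between trials would enlarge the artefact.
- **Residual confounding.** Splitting by trial does not give a randomised comparison. In ORACLE MS, open-label cladribine followed McDonald conversion and open-label interferon was offered on CDMS conversion (SAP 6.2). In CLARITY, staying never exposed depended on not entering the extension. This stands and limits what the fix can claim.

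A reader might infer that trial mix drives the curves, or that the bias necessarily runs against cladribine. The documents do not support either: they give no exposure-by-trial counts, trial-specific risks or open-label uptake. A reader might also say the overall curve describes no real population, but Cohort A is the study's own defined pooled cohort.

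**Conclusion.** The point holds as possible confounding by parent trial in the pooled exposed versus never-exposed Kaplan-Meier, ARR, bedridden and SPMS outputs. The plan neither stratifies nor adjusts for trial in these, although it adjusts the primary endpoint for trial and tabulates the primary and EDSS 6.0 or higher endpoints by cohort.

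A difference in trial mix is probable from the parent designs. Under the assumptions above it is 40-57% versus 26-31% ORACLE MS, with a spurious risk ratio of 1.11-1.46 at the 10%/2% risks. These figures are illustrative. They depend on extension entry in the placebo arm, open-label uptake and trial-specific risks, none of which the documents report. I have put no figure on the ARR or SPMS outputs. This is a cheap improvement to interpretability, not a fault that invalidates the analysis.

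**What to change.** 1. Repeat Tables 15.2.6.1-2 and Figures 15.2.6.1-2 for Cohort B and Cohort D, and show the exposed and never-exposed counts by parent trial beside them.
2. Standardise any pooled Cohort A exposed versus never-exposed display to one parent-trial mix, using trial-weighted curves, ARR and proportions with the same weights in both groups.
3. State next to these outputs that this removes between-trial confounding only, because exposure within each trial also depends on extension entry or conversion. The trial-specific results should not be presented as unconfounded.

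The cost is more outputs, re-running existing programs on cohorts already defined in the SAP, a modest amount of programming for the weighted display, and wider intervals within each trial.
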